- The absolute values and relative rate of decline of Speech related endpoints along with the absolute values and relative rate of decline of ALSFRS-R total score and FVC values will be plotted against time (X), respectively.

- **Correlation Analysis**

An estimate of the between-subject correlation and the within-subject correlation will be obtained using the method described in [Roy, 2006](#). The between-subject correlation will characterize whether subjects with greater decrease in the endpoint also tend to have the greater change in ALSFRS-R. The within-subject correlation will describe whether a decrease in one endpoint within an individual is associated with a decrease in the other endpoint.

A mixed effect model with the change from baseline in the endpoints and the change from baseline in the ALSFRS-R score as dependent variables will be fitted. An indicator variable to distinguish the two endpoints will be fitted as a fixed effect and a random effect. Other explanatory covariates will be fitted as fixed effects, as appropriate.

The RANDOM and REPEATED statements will be used to specify the structure of the covariance matrix for the two responses. The RANDOM statement will be used to specify an unstructured variance-covariance structure for the two responses. The REPEATED statement will be used to specify the variance covariance matrix for the error terms in the model. The structure of the variance covariance matrix is constructed by taking the Kronecker product of an unstructured matrix, which models the covariance for the two endpoints, with an unstructured or autoregressive (AR (1)) covariance matrix which models the covariance for the 2 repeated measures across visits.

If the data is not sufficient to allow for convergence of the model, then alternative variance covariance matrices may be considered. If convergence of the model parameters still cannot be achieved, the approach by [Bland, 1995](#) will be used to estimate the within subject correlation.

- **Actigraphy**

- The absolute values and change from baseline for the actigraphy endpoints will be analyzed for correlation with absolute values and change from baseline of Total score of ALSFRS-R, respectively.

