- The absolute values and change from baseline in the time spent active (day only), Time Spent sedentary not lying (day only), Time Spent Lying (day only), Time Spent Sedentary (day only), Total Activity Score (By 24 Hour and by Day), Maximum Score (By 24 Hour and by Day), Active Periods (Numbers) (day only), Active Periods (Duration) (day only) will be analysed for correlation with the absolute values and change from

Statistical Analyses	

 ○ Heart Rate Variability 
 ▪ The absolute values and change from baseline in the heart rate variability endpoints will be analyzed for correlation with the absolute values and change from baseline in the Total score of ALSFRS-R, respectively. ▪ For the above endpoints analyzed for correlation, scatter plots will be done ○ Speech assessment 
 ▪ The absolute values and change from baseline in the speech endpoints will be analyzed for correlation with the absolute values and change from baseline in the Total ALSFRS-R, respectively. ▪ The absolute values and change from baseline in the speech endpoints will be analyzed for correlation with the absolute values and change from baseline of bulbar domain and respiratory domain of ALSFRS-R, respectively. ▪ The absolute values and change from baseline in the speech endpoints will be analyzed for correlation with the absolute values and change from baseline in the FVC, respectively. 	
baseline to the-gross motor domain and fine motor domain of ALSFRS-R, respectively.
 
For the above endpoints analyzed for correlation, scatter plots will be done
 
The correlation analysis will be performed on both non normalized and normalized data. Only the quality data (i.e. the data without the data quality deviators as defined in Section 7.1.1) will be used for the statistical analysis.
 
Only the quality data will be used for the statistical analysis.
 
Only the quality data will be used for the statistical analysis.

Model Results Presentation	

 ● Descriptive Statistics 
 ○ Data listings ○ Summary tables ○ Visualization graphs ● Correlation Analysis 
 ○ Result tables ○ Visualization graphs 	

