9.4.3. Exploratory

ALSFRS-R Total Score

The ALS functional rating scale – revised (ALSFRS-R) assesses the functioning of ALS subjects across 4 domains: gross motor activity, fine motor activity, bulbar and respiratory function. The ALSFRS-R [Cedarbaum, 1999] consists of 12 questions each of which are scored on a 5-point scale from 0-4, where 4 is the best possible outcome and 0 is the worst.
 
The total score will be calculated by summing responses to each of the 12 individual questions. The maximum total score is therefore 48, lower scores indicate worse functioning. If there are any missing questions, then the total score will be set to missing.
 
ALSFRS will be grouped to four different domains: Fine motor, Gross motor, Respiratory and Bulbar Domain [Cedarbaum, 1999]

FVC

FVC is a measure of respiratory function and is the volume of air that can forcibly be blown out after a single, full breath. FVC is a sensitive measure of ALS disease progression, is used as a standard test for ALS management, and is recommended as a secondary outcome measure in ALS clinical trials [Cudkowicz, 2004; Czaplinski, 2006; Clavelou, 2013].
 
FVC will be performed by experienced site personnel according to local protocol using a calibrated spirometer. Every effort should be made to have the same individual perform the FVC for a given subject throughout the study. For each time point, the best FVC result (in litres) will be recorded in the eCRF.

Relative Rate of Decline and Monthly Rate of Decline (Slope)

Relative Rate of Decline = $\frac{\text{Value at a time point} - \text{Value at the Baseline}}{\text{Value at the Baseline}}$
 
 $\frac{\text{Monthly rate of decline at each visit} = \frac{\text{Change from baseline of the endpoint at each post-baseline visit}}{\text{Study day}/30.4}}$ 
 
Monthly Rate of Decline= Average of Monthly Rate of Decline at each visit and is populated only for the last visit.
 
For Monthly Rate of Decline, if an assessment took place over a number of consecutive days then the average of that will be taken and the recent visit (last time point) will be considered to calculate study day.

Actigraphy

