 - Central tendency of fundamental F0, relative jitter, relative shimmer
- Long ah
 - Central tendency of fundamental F0, relative jitter, relative shimmer
- Single word – doily
 - Average phoneme rate, average phonation time
- Running speech (bamboo passage)
 - Speaking rate % pause time

CODE	DESCRIPTION
AA001	Central tendency of fundamental F0 (code 001: short ah) HZ (code 002: long ah) ?? middle five seconds of the phonation interval??
AA002	Relative Jitter (code 001: short ah) % (code 002: long ah)
AA003	Relative Shimmer (code 001: short ah)

%	(code 002: long ah)
AA004 (Hz/s)	Average phoneme rate (Phoneme – subpart of word) code 003: “single word” doily
AA005 (s)	Average phonation time code 003: “single word” doily
AA007 %	% pause time (Code 004: running speech)
AA008 (WPM)	Speaking rate (Code 004: running speech)

Heart Rate Variability (all LF/HF HRV metrics are over 5 minutes’ windows)

HRV data are captured for each of the activity classifiers: Active + Lying + “sedentary not lying”. “Lying minus active” and “Lying minus sedentary not lying” is derived based on the following:

MLFHFN	Mean LF/HF (Avg over 5 min windows of lying down)	Use the sum of the means over each recording day (Day 1 + Day 2 + Day 3) divided by the total number of recording points over the 3 days (number Day 1+2+3) (number of lying periods of good enough quality to obtain HRV from)
VLFHFN	Var of LF/HF (Avg over 5 min windows of lying down)	Use the sum of the variances over each recording day (Day 1 + Day 2 + Day 3) divided by the total number of recording points over the 3 days (number Day 1+2+3) (number of lying periods of good

		enough quality to obtain HRV from)
MLFHFSD	Mean LF/HF (avg-stationary-day) Stationary = sedentary not lying	Derive 1 average value for each protocol time point, Use the sum of the means over each recording day (Day 1 + Day 2 + Day 3) divided by the total number of recording points over the 3 days (number Day 1+2+3) (number of 'sedentary not lying' periods of good enough quality to obtain HRV from)
VLHFSD	Var of LF/HF (avg-stationary-day) Stationary = sedentary not lying	Derive 1 average value for each protocol time point, Use the sum of the variances over each recording day divided by the total number of recording points (number of 'sedentary not lying' periods of good enough quality to obtain HRV from)

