9.7. Appendix 7: Examination of Covariates, Subgroups & Other Strata

9.7.1. Handling of Covariates, Subgroups & Other Strata

There was no randomisation and therefore no strata used in this study.

Due to the small number of subjects in the study, no subgroups will be specified here although subgroup analyses may take place ad hoc.

The following is a list of covariates that may be used in descriptive summaries and/ or statistical analyses (See Section 7.1.1 and Section 7.1.2 for further details).

Additional covariates of clinical interest may also be considered.

These analyses will be carried out as part of ADHOC if necessary.

Category	Covariates and / or Subgroups
Correlation of ALSFRS-R and movement actigraphy data/ HRV data	In additional to the model described in Section 7.1.2, the following explanatory variables may be considered: 
 • Baseline value for each of the dependent variables being correlated • Phenotype at onset: Bulbar/Limb/Other • Age at baseline • Sex – Male/ Female • Time since onset of muscle weakness
Correlation of FVC/ ALSFRS-R and speech data	In additional to the model described in Section 7.1.2, the following explanatory variables may be considered: 
 • Baseline value for each of the dependent variables being correlated • Phenotype at onset: Bulbar/Limb/Other • Smoking status at baseline • Age at baseline • Sex – Male/ Female • Time since onset of muscle weakness
Mixed model repeated measures analyses	For the MMRM Baseline, Visit, Baseline by Visit covariates will be included in model. The following explanatory variables may also be considered: 
 • Phenotype at onset: Bulbar or Other/ Limb • Smoking status at baseline • Age at baseline • Sex – Male/ Female • Time since onset of muscle weakness

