
Efficacy: Tables					
No.	Population	IDSL / TST ID / Example Shell	Title	Programming Notes	Deliverable [Priority]
2.132.	FAS	EFF_T3	Statistical Analysis of Relationship between Slope of RMSSD and Slope of Total ALSFRS-R		SAC
Speech					
2.133.	FAS	EFF_T1	Summary of Speech Endpoints	Categorise by Test	SAC
2.134.	FAS	EFF_T1	Summary of Change from Baseline of Speech Endpoints	Categorise by Test	SAC
2.135.	FAS	EFF_T1	Summary of Relative Rate of Decline of Speech Endpoints	Categorise by Test	SAC
2.136.	FAS	EFF_T1	Summary of Monthly Rate of Speech Endpoints	Categorise by Test	SAC
2.137.	FAS	EFF_T3	Statistical Analysis of Relationship between Absolute Values of Speech endpoints and Absolute Value of ALSFRS-R	Paginate by Total Score of ALSFRS, Bulbar Domain and Respiratory Domain	SAC
2.138.	FAS	EFF_T3	Statistical Analysis of Relationship between Change from Baseline of Speech endpoints and Change from Baseline of ALSFRS-R	Paginate by Total Score of ALSFRS, Bulbar Domain and Respiratory Domain	SAC
2.139.	FAS	EFF_T3	Statistical Analysis of Relationship between Slope of Speech endpoints and Slope of ALSFRS-R	Paginate by Total Score of ALSFRS, Bulbar Domain and Respiratory Domain	SAC
2.140.	FAS	EFF_T3	Statistical Analysis of Relationship Absolute Values of Speech endpoints and Absolute Values of FVC		SAC
2.141.	FAS	EFF_T3	Statistical Analysis of Relationship between Change from Baseline of Speech endpoints and Change from Baseline of FVC		SAC
2.142.	FAS	EFF_T3	Statistical Analysis of Relationship between Slope of Speech endpoints and Slope of FVC		SAC
Data Quality Deviator					
2.143.	FAS	EFF_T2	Summary of Data Quality Deviators of Actigraphy Data	Footnote the 3 Rules	SAC
2.144.	FAS	EFF_T2	Summary of Data Quality Deviators of HRV Data	Footnote the 3 Rules	SAC

Efficacy: Tables					
No.	Population	IDSL / TST ID / Example Shell	Title	Programming Notes	Deliverable [Priority]
Reconciliation of Actigraphy and Diary Data					
2.145.	FAS	EFF_T2	Summary of Reconciliation of Actigraphy and Diary Data	Footnote: 3 Rules N is the number of subjects at each visit	SAC
Actigraphy Diary – Feasibility Measures					
2.146.	FAS	EFF_T4	Summary of Actigraphy Diary (Feasibility) Data		SAC
Device Impact– Feasibility Measures					
2.147.	FAS	EFF_T5	Summary of Device Impact		SAC
ALSFRS-R					
2.148.	FAS	EFF_T1	Summary of ALSFRS-R Score	Paginate by Total Score, Gross Motor Domain, Fine Motor Domain, Bulbar Domain and Respiratory Domain	SAC

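### Sex adjustment is optional, ad hoc and conditional for the between-subject correlation of absolute speech measures (chiefly F0) with FVC in litres

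*SAP*

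**What the plan says.** Section 7.1.2 plans that speech endpoints, as absolute values and as changes, are "analyzed for correlation with the absolute values and change from baseline in the FVC, respectively". Table 2.140 in Section 9.11.4, titled "Statistical Analysis of Relationship Absolute Values of Speech endpoints and Absolute Values of FVC", is the absolute-value deliverable; its programming note is empty.

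On scale, Section 9.4.3 states: "For each time point, the best FVC result (in litres) will be recorded in the eCRF". No percent-predicted or otherwise standardised FVC is defined. The speech code list in the same section has the entry "Central tendency of fundamental F0 (code 001: short ah) HZ", with a second code for the long ah.

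On the model, Section 7.1.2 says: "An estimate of the between-subject correlation and the within-subject correlation will be obtained using the method described in" the cited mixed-model paper. The only fixed effect it names is the indicator that separates the two responses. For anything else it says "Other explanatory covariates will be fitted as fixed effects, as appropriate".

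On sex, Section 9.7.1 has a row for the correlation of speech with FVC or ALSFRS-R. Sex and age at baseline are on its list of variables open to consideration. The section adds: "These analyses will be carried out as part of ADHOC if necessary". The synopsis makes the Section 9.7 work follow from a correlation found in the first step. Section 9.8 judges relationships by the size of the coefficient, with no threshold and no multiplicity adjustment.

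**The concern.** A between-subject correlation of raw values picks up any trait that shifts both variables. If men and women differ in F0 and in FVC in litres for reasons unrelated to ALS, pooling them adds a component that says nothing about disease. Where women have the higher F0 and the lower FVC, that component is negative.

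Two misreadings are possible. A coefficient produced by the sex mix could be taken as speech tracking respiratory function. Conversely, a real positive relation within each sex could be cancelled or reversed. The second is harder to recover from, because the step in which sex might be fitted is reached only when the unadjusted coefficient already shows a correlation. The stake is interpretation and the choice of markers to pursue; the study tests no formal hypothesis.

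**Working it through.** The SAP states no correlation, sample size or sex difference for this point, so there is no figure of its own to reproduce. The check is an illustration under assumptions.

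**From the SAP:** absolute FVC in litres and F0 in Hz (Section 9.4.3); a between-subject coefficient with no named covariate (Section 7.1.2).

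**Assumed (not in the SAP):** share of women p = 0.35 or 0.50; F0 gap d1 (women minus men) of 1 to 3 within-sex SD; FVC gap d2 (men minus women) of 0.5 to 2 within-sex SD; within-sex correlation r_w.

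**Formula.** With k = p(1 - p), the pooled correlation is

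r = (r_w - k·d1·d2) / sqrt[(1 + k·d1²)(1 + k·d2²)]

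**No relation within sex (r_w = 0):**

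| Women | F0 gap | FVC gap 0.5 | 1 | 1.5 | 2 |
|---|---|---|---|---|---|
| 50% | 1 | -0.11 | -0.20 | -0.27 | -0.32 |
| 50% | 2 | -0.17 | -0.32 | -0.42 | -0.50 |
| 50% | 3 | -0.20 | -0.37 | -0.50 | -0.59 |
| 35% | 1 | -0.10 | -0.19 | -0.25 | -0.30 |
| 35% | 2 | -0.16 | -0.30 | -0.40 | -0.48 |
| 35% | 3 | -0.19 | -0.35 | -0.48 | -0.57 |

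The two extremes in full:
- p = 0.35, d1 = 1, d2 = 0.5: k = 0.2275, so r = -0.11375 / sqrt(1.2275 × 1.0569) = -0.10.
- p = 0.50, d1 = 3, d2 = 2: k = 0.25, so r = -1.5 / sqrt(3.25 × 2) = -0.59.

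If either gap is zero, the induced correlation is zero.

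**A real relation within sex (p = 0.50, d1 = 2, d2 = 1):**
- r_w = 0.5: the numerator is 0.5 - 0.25 × 2 × 1 = 0, so r = 0.00.
- r_w = 0.3: r = (0.3 - 0.5) / sqrt(2 × 1.25) = -0.13.

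**Effect of adjustment.** In a simulation of 400,000 subjects with p = 0.35, d1 = 3 and d2 = 1.5, removing the sex mean from each response returned the within-sex value. With r_w = 0 the coefficient was -0.48 unadjusted and 0.00 adjusted; with r_w = 0.5 it was -0.24 unadjusted and 0.50 adjusted. The unadjusted values agree with the formula.

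**Scope.** Section 9.4.3 lists ten test-measure combinations: three for the short ah, three for the long ah, two for the single word and two for running speech. F0 is two of the ten. A constant sex gap subtracts out of change from baseline and does not enter the within-subject correlation.

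**The case against.** The plan does not ignore sex. Section 7.1.2 leaves room for covariates, and Section 9.7.1 names sex and age for exactly this correlation. A reader might infer from Table 2.140 alone that sex adjustment is excluded; the documents do not support that. It is permitted, but not committed. For a spurious coefficient there is also some protection, since an apparent correlation is what triggers the step in which sex can be considered. That protection is incomplete, because fitting sex remains optional even then, and it fails altogether when sex masks a relation.

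The reach is also limited. A reader might extend the point to every speech-FVC analysis. The stated hypothesis in Section 2.4 concerns change against change, and the model text in Section 7.1.2 is written for changes from baseline. Those results and the within-subject coefficients are largely untouched. For the eight combinations other than F0, no sex gap has been put forward. These limits stand.

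Finally, the study is small, and Section 7.1.2 already foresees convergence trouble, so extra terms are not free. This argues for a lean adjustment rather than for none.

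**Conclusion.** The point holds for the between-subject coefficient in Table 2.140, for speech measures that differ by sex, chiefly F0. The only committed version of that coefficient has no prespecified sex effect, and the route to an adjusted one depends on the unadjusted result.

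Under the assumed gaps and sex mix, the induced coefficient is about -0.10 to -0.59, that is, weak to moderate and negative. A true within-sex correlation of 0.5 falls to about 0 in the equal-sex case with gaps of 2 and 1 SD. These are large-sample values. A wide spread of disease severity would enlarge the within-sex SDs and move the result towards the lower end.

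One might infer that a moderate spurious correlation is to be expected here. The SAP gives neither the sex mix nor the sex differences, so the calculation shows what can happen, not what will. Nor is an error rate affected: there is no primary endpoint and no formal test. It is still worth correcting before analysis, because Section 9.8 makes the size of the coefficient the basis for judgement.

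**What to change.** Amend Section 7.1.2 so that the planned absolute-value speech-FVC models include sex and its interaction with the endpoint indicator, giving each response its own sex effect. Add a programming note to Table 2.140 asking for the unadjusted and sex-adjusted between-subject coefficients side by side for each speech measure. State that the adjusted coefficient is produced whatever the first-step result, so that it does not depend on the condition in the synopsis. Age at baseline can be a sensitivity analysis; no calculation here shows that it is needed in the main model.

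The cost is SAP wording, an extra column in one table and one extra parameter per response. In a small study this loses a little precision and may add to convergence problems. Sex is already listed in Section 9.7.1, so the SAP itself treats it as available.

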9.11.5. Exploratory Figures

Exploratory: Figures					
No.	Population	IDSL / TST ID / Example Shell	Title	Programming Notes	Deliverable [Priority]
Actigraphy					
2.1.	FAS	EFF_F1	Plot of Absolute Values of Time Spent Active and Absolute Value of ALSFRS-R v/s Time (All data)	Plot Time on X Axis, Endpoint on Y axis and ALSFRS on RHS of Y axis ALSFRS: Total, Fine Motor and Gross Motor	SAC
2.2.	FAS	EFF_F1	Plot of Absolute Values of Time Spent Active and Absolute Value of ALSFRS-R v/s Time (Quality data)	Same as Above	SAC
2.3.	FAS	EFF_F1	Plot of Relative Rate of Decline of Time Spent Active and Relative Rate of Decline of ALSFRS-R v/s Time (All data)	Same as Above	SAC
2.4.	FAS	EFF_F1	Plot of Relative Rate of Decline of Time Spent Active and Relative Rate of Decline of ALSFRS-R v/s Time (Quality data)	Same as Above	SAC
2.5.	FAS	EFF_F1	Plot of Absolute Values of Overall Time Spent Sedentary Not Lying and Absolute Value of ALSFRS-R v/s Time (All data)	Same as Above	SAC
2.6.	FAS	EFF_F1	Plot of Absolute Values of Overall Time Spent Sedentary Not Lying and Absolute Value of ALSFRS-R v/s Time (Quality data)	Same as Above	SAC
2.7.	FAS	EFF_F1	Plot of Relative Rate of Decline of Overall Time Spent Sedentary Not Lying and Relative Rate of Decline of ALSFRS-R v/s Time (All data)	Same as Above	SAC

CONFIDENTIAL

201283

Exploratory: Figures					
No.	Population	IDSL / TST ID / Example Shell	Title	Programming Notes	Deliverable [Priority]
2.8.	FAS	EFF_F1	Plot of Relative Rate of Decline of Overall Time Spent Sedentary Not Lying and Relative Rate of Decline of ALSFRS-R v/s Time (Quality data)	Same as Above	SAC
2.9.	FAS	EFF_F1	Plot of Absolute Values of Time Spent Lying and Absolute Value of ALSFRS-R v/s Time (All data)	Same as Above	SAC
2.10.	FAS	EFF_F1	Plot of Absolute Values of Time Spent Lying and Absolute Value of ALSFRS-R v/s Time (Quality data)	Same as Above	SAC
2.11.	FAS	EFF_F1	Plot of Relative Rate of Decline of Time Spent Lying and Relative Rate of Decline of ALSFRS-R v/s Time (All data)	Same as Above	SAC
2.12.	FAS	EFF_F1	Plot of Relative Rate of Decline of Time Spent Lying and Relative Rate of Decline of ALSFRS-R v/s Time (Quality data)	Same as Above	SAC
2.13.	FAS	EFF_F1	Plot of Absolute Values of Time Spent Sedentary and Absolute Value of ALSFRS-R v/s Time (All data)	Same as Above	SAC
2.14.	FAS	EFF_F1	Plot of Absolute Values of Time Spent Sedentary and Absolute Value of ALSFRS-R v/s Time (Quality data)	Same as Above	SAC
2.15.	FAS	EFF_F1	Plot of Relative Rate of Decline of Time Spent Sedentary and Relative Rate of Decline of ALSFRS-R v/s Time (All data)	Same as Above	SAC

CONFIDENTIAL

201283

Exploratory: Figures					
No.	Population	IDSL / TST ID / Example Shell	Title	Programming Notes	Deliverable [Priority]
2.16.	FAS	EFF_F1	Plot of Relative Rate of Decline of Time Spent Sedentary and Relative Rate of Decline of ALSFRS-R v/s Time (Quality data)	Same as Above	SAC
2.17.	FAS	EFF_F1	Plot of Absolute Values of Total Activity Score Day/Night and Absolute Value of ALSFRS-R v/s Time (All data)	Same as Above	SAC
2.18.	FAS	EFF_F1	Plot of Absolute Values of Total Activity Score Day/Night and Absolute Value of ALSFRS-R v/s Time (Quality data)	Same as Above	SAC
2.19.	FAS	EFF_F1	Plot of Relative Rate of Decline of Total Activity Score Day/Night and Relative Rate of Decline of ALSFRS-R v/s Time (All data)	Same as Above	SAC
2.20.	FAS	EFF_F1	Plot of Relative Rate of Decline of Total Activity Score Day/Night and Absolute Value of ALSFRS-R v/s Time (Quality data)	Same as Above	SAC
2.21.	FAS	EFF_F1	Plot of Absolute Values of Total Activity Score – 24 Hour and Absolute Value of ALSFRS-R v/s Time (All data)	Same as Above	SAC
2.22.	FAS	EFF_F1	Plot of Absolute Values of Total Activity Score – 24 Hour and Absolute Value of ALSFRS-R v/s Time (Quality data)	Same as Above	SAC
2.23.	FAS	EFF_F1	Plot of Relative Rate of Decline of Total Activity Score – 24 Hour and Relative Rate of Decline of ALSFRS-R v/s Time (All data)	Same as Above	SAC

CONFIDENTIAL

201283

Exploratory: Figures					
No.	Population	IDSL / TST ID / Example Shell	Title	Programming Notes	Deliverable [Priority]
2.24.	FAS	EFF_F1	Plot of Relative Rate of Decline of Total Activity Score – 24 Hour and Relative Rate of Decline of ALSFRS-R v/s Time (Quality data)	Same as Above	SAC
2.25.	FAS	EFF_F1	Plot of Absolute Values of Maximum Score (1 min – 24 Hour Window) and Absolute Value of ALSFRS-R v/s Time (All data)	Same as Above	SAC
2.26.	FAS	EFF_F1	Plot of Absolute Values Maximum Score (1 min – 24 Hour Window) and Absolute Value of ALSFRS-R v/s Time (Quality data)	Same as Above	SAC
2.27.	FAS	EFF_F1	Plot of Relative Rate of Decline of Maximum Score (1 min – 24 Hour Window) and Relative Rate of Decline of ALSFRS-R v/s Time (All data)	Same as Above	SAC
2.28.	FAS	EFF_F1	Plot of Relative Rate of Decline of Maximum Score (1 min – 24 Hour Window) and Relative Rate of Decline of ALSFRS-R v/s Time (Quality data)	Same as Above	SAC
2.29.	FAS	EFF_F1	Plot of Absolute Values of Active Periods (Number) and Absolute Value of ALSFRS-R v/s Time (All data)	5-day time lines (1 for each category) vs ALSFRS on 1 page 5-night time lines vs ALSFRS on 2 nd page	SAC
2.30.	FAS	EFF_F1	Plot of Absolute Values of Active Periods (Number) and Absolute Value of ALSFRS-R v/s Time (Quality data)	5-day time lines (1 for each category) vs ALSFRS on 1 page 5-night time lines vs ALSFRS on 2 nd page	SAC

Exploratory: Figures					
No.	Population	IDSL / TST ID / Example Shell	Title	Programming Notes	Deliverable [Priority]
2.31.	FAS	EFF_F1	Plot of Active Periods (Number)	Plot of number (y) over time (x)	SAC
2.32.	FAS	EFF_F1	Plot of Active Periods (Number) and ALSFRS-R v/s Time	5-day time lines (1 for each category) vs ALSFRS on 1 page 5-night time lines vs ALSFRS on 2 nd page	SAC
2.33.	FAS	EFF_F1	Plot of Absolute Values of Active Periods (Duration) and Absolute Value of ALSFRS-R v/s Time (All data)	Plot Time on X Axis, Endpoint on Y axis and ALSFRS on RHS of Y axis ALSFRS: Total, Fine Motor and Gross Motor	SAC
2.34.	FAS	EFF_F1	Plot of Absolute Values of Active Periods (Duration) and Absolute Value of ALSFRS-R v/s Time (Quality data)	Same as Above	SAC
2.35.	FAS	EFF_F1	Plot of Relative Rate of Decline of Active Periods (Duration) and Relative Rate of Decline of ALSFRS-R v/s Time (All data)	Same as Above	SAC
2.36.	FAS	EFF_F1	Plot of Relative Rate of Decline of Active Periods (Duration) and Relative Rate of Decline of ALSFRS-R v/s Time (Quality data)	Same as Above	SAC
2.37.	FAS	EFF_F2	Scatter Plot of Absolute Values of Actigraphy endpoints and Absolute Value of Total ALSFRS-R	Plot the individual values as dots	SAC
2.38.	FAS	EFF_F2	Scatter Plot of Change from Baseline of Actigraphy endpoints and Change from Baseline of Total ALSFRS-R	Plot the individual values as dots	SAC

Exploratory: Figures					
No.	Population	IDSL / TST ID / Example Shell	Title	Programming Notes	Deliverable [Priority]
2.39.	FAS	EFF_F2	Scatter Plot of Slope of Actigraphy endpoints and Slope of Total ALSFRS-R	Plot the individual values as dots	SAC
2.40.	FAS	EFF_F2	Scatter Plot of Absolute Values of Actigraphy endpoints and Absolute Value of gross motor domain of ALSFRS-R	Plot the individual values as dots	SAC
2.41.	FAS	EFF_F2	Scatter Plot of Change from Baseline of Actigraphy endpoints and Change from Baseline of gross motor domain of ALSFRS-R	Plot the individual values as dots	SAC
2.42.	FAS	EFF_F2	Scatter Plot of Slope of Actigraphy endpoints and Slope of gross motor domain of ALSFRS-R	Plot the individual values as dots	SAC
2.43.	FAS	EFF_F2	Scatter Plot of Absolute Values of Actigraphy endpoints and Absolute Value of fine motor domain of ALSFRS-R	Plot the individual values as dots	SAC
2.44.	FAS	EFF_F2	Scatter Plot of Change from Baseline of Actigraphy endpoints and Change from Baseline of fine motor domain of ALSFRS-R	Plot the individual values as dots	SAC
2.45.	FAS	EFF_F2	Scatter Plot of Slope of Actigraphy endpoints and Slope of fine motor domain of ALSFRS-R	Plot the individual values as dots	SAC
Night Time Rest Endpoints					
2.46.	FAS	EFF_F1	Plot of Absolute Values of Number Night Time Movement and Absolute Value of ALSFRS-R v/s Time (All data)	Plot Time on X Axis, Endpoint on Y axis and ALSFRS on RHS of Y axis ALSFRS: Total	SAC
2.47.	FAS	EFF_F1	Plot of Absolute Values of Number Night Time Movement and Absolute Value of ALSFRS-R v/s Time (Quality data)	Same as Above	SAC
2.48.	FAS	EFF_F1	Plot of Relative Rate of Decline of Number Night Time Movement and Relative Rate of Decline of ALSFRS-R v/s Time (All data)	Same as Above	SAC

CONFIDENTIAL

201283

Exploratory: Figures					
No.	Population	IDSL / TST ID / Example Shell	Title	Programming Notes	Deliverable [Priority]
2.49.	FAS	EFF_F1	Plot of Relative Rate of Decline of Number Night Time Movement and Relative Rate of Decline of ALSFRS-R v/s Time (Quality data)	Same as Above	SAC
2.50.	FAS	EFF_F1	Plot of Absolute Values of Night-time Rest Efficiency and Absolute Value of ALSFRS-R v/s Time (All data)	Same as Above	SAC
2.51.	FAS	EFF_F1	Plot of Absolute Values of Night-time Rest Efficiency and Absolute Value of ALSFRS-R v/s Time (Quality data)	Same as Above	SAC
2.52.	FAS	EFF_F1	Plot of Relative Rate of Decline of Night-time Rest Efficiency and Relative Rate of Decline of ALSFRS-R v/s Time (All data)	Same as Above	SAC
2.53.	FAS	EFF_F1	Plot of Relative Rate of Decline of Night-time Rest Efficiency and Relative Rate of Decline of ALSFRS-R v/s Time (Quality data)	Same as Above	SAC
2.54.	FAS	EFF_F1	Plot of Absolute Values of Rest Fragmentation Index and Absolute Value of ALSFRS-R v/s Time (All data)	Same as Above	SAC
2.55.	FAS	EFF_F1	Plot of Absolute Values of Rest Fragmentation Index and Absolute Value of ALSFRS-R v/s Time (Quality data)	Same as Above	SAC
2.56.	FAS	EFF_F1	Plot of Relative Rate of Decline of Rest Fragmentation Index and Relative Rate of Decline of ALSFRS-R v/s Time (All data)	Same as Above	SAC

Exploratory: Figures					
No.	Population	IDSL / TST ID / Example Shell	Title	Programming Notes	Deliverable [Priority]
2.57.	FAS	EFF_F1	Plot of Relative Rate of Decline of Rest Fragmentation Index and Relative Rate of Decline of ALSFRS-R v/s Time (Quality data)	Same as Above	SAC
2.58.	FAS	EFF_F1	Plot of Absolute Values of Duration Movement Episodes and Absolute Value of ALSFRS-R v/s Time (All data)	Same as Above	SAC
2.59.	FAS	EFF_F1	Plot of Absolute Values of Duration Movement Episodes and Absolute Value of ALSFRS-R v/s Time (Quality data)	Same as Above	SAC
2.60.	FAS	EFF_F1	Plot of Relative Rate of Decline of Duration Movement Episodes and Relative Rate of Decline of ALSFRS-R v/s Time (All data)	Same as Above	SAC
2.61.	FAS	EFF_F1	Plot of Relative Rate of Decline of Duration Movement Episodes and Relative Rate of Decline of ALSFRS-R v/s Time (Quality data)	Same as Above	SAC
2.62.	FAS	EFF_F2	Scatter Plot of Absolute Values of Night Rest Endpoints and Absolute Value of Total ALSFRS-R	Plot the individual values as dots	SAC
2.63.	FAS	EFF_F2	Scatter Plot of Change from Baseline of Night Rest Endpoints and Change from Baseline of Total ALSFRS-R	Plot the individual values as dots	SAC
2.64.	FAS	EFF_F2	Scatter Plot of Slope of Night Rest Endpoints and Slope of Total ALSFRS-R	Plot the individual values as dots	SAC
Heart Rate Variability					
2.65.	FAS	EFF_F1	Plot of Absolute Values of Mean HRV LF/HF and Absolute Value of ALSFRS-R v/s Time (All data)	Plot Time on X Axis, Endpoint on Y axis and ALSFRS on RHS of Y axis ALSFRS: Total	SAC

Exploratory: Figures					
No.	Population	IDSL / TST ID / Example Shell	Title	Programming Notes	Deliverable [Priority]
2.66.	FAS	EFF_F1	Plot of Relative Rate of Decline of Mean HRV LF/HF and Relative Rate of Decline of ALSFRS-R v/s Time (All data)	Same as Above	SAC
2.67.	FAS	EFF_F1	Plot of Absolute Values of Mean RMSSD and Absolute Value of ALSFRS-R v/s Time (All data)	Same as Above	SAC
2.68.	FAS	EFF_F1	Plot of Absolute Values of Mean RMSSD and Absolute Value of ALSFRS-R v/s Time (Quality data)	Same as Above	SAC
2.69.	FAS	EFF_F1	Plot of Relative Rate of Decline of Mean RMSSD and Relative Rate of Decline of ALSFRS-R v/s Time (All data)	Same as Above	SAC
2.70.	FAS	EFF_F1	Plot of Relative Rate of Decline of Mean RMSSD and Relative Rate of Decline of ALSFRS-R v/s Time (Quality data)	Same as Above	SAC
2.71.	FAS	EFF_F1	Plot of Absolute Values of Variance HRV LF/HF and Absolute Value of ALSFRS-R v/s Time (All data)	Same as Above	SAC
2.72.	FAS	EFF_F1	Plot of Relative Rate of Decline of Variance HRV LF/HF and Relative Rate of Decline of ALSFRS-R v/s Time (All data)	Same as Above	SAC
2.73.	FAS	EFF_F1	Plot of Absolute Values of Variance RMSSD and Absolute Value of ALSFRS-R v/s Time (All data)	Same as Above	SAC

Exploratory: Figures					
No.	Population	IDSL / TST ID / Example Shell	Title	Programming Notes	Deliverable [Priority]
2.74.	FAS	EFF_F1	Plot of Absolute Values of Variance RMSSD and Absolute Value of ALSFRS-R v/s Time (Quality data)	Same as Above	SAC
2.75.	FAS	EFF_F1	Plot of Relative Rate of Decline of Variance RMSSD and Relative Rate of Decline of ALSFRS-R v/s Time (All data)	Same as Above	SAC
2.76.	FAS	EFF_F1	Plot of Relative Rate of Decline of Variance RMSSD and Relative Rate of Decline of ALSFRS-R v/s Time (Quality data)	Same as Above	SAC
2.77.	FAS	EFF_F2	Scatter Plot of Absolute Values of HRV endpoints (LF/HF) and Absolute Value of Total ALSFRS-R	Plot individual values as dots	SAC
2.78.	FAS	EFF_F2	Scatter Plot of Absolute Values of RMSSD and Absolute Value of Total ALSFRS-R	Plot individual values as dots	SAC
2.79.	FAS	EFF_F2	Scatter Plot of Change from Baseline of HRV endpoints (LF/HF) and Change from Baseline of Total ALSFRS-R	Plot individual values as dots	SAC
2.80.	FAS	EFF_F2	Scatter Plot of Change from Baseline of RMSSD and Change from Baseline of Total ALSFRS-R	Plot individual values as dots	SAC
2.81.	FAS	EFF_F2	Scatter Plot of Slope of HRV endpoints (LF/HF) and Slope of Total ALSFRS-R	Plot individual values as dots	SAC
2.82.	FAS	EFF_F2	Scatter Plot of Slope of RMSSD and Slope of Total ALSFRS-R	Plot individual values as dots	SAC
Speech					
2.83.	FAS	EFF_F1	Plot of Absolute Values of Speech Endpoints and Absolute Values of ALSFRS-R v/s Time	Plot Time on X Axis, Endpoint on Y axis and ALSFRS on RHS of Y axis ALSFRS: Total Bulbar and Respiratory Domain	SAC

Exploratory: Figures					
No.	Population	IDSL / TST ID / Example Shell	Title	Programming Notes	Deliverable [Priority]
2.84.	FAS	EFF_F1	Plot of Relative Rate of decline of Speech Endpoints and Relative Rate of decline of ALSFRS-R v/s Time	Same as Above	SAC
2.85.	FAS	EFF_F2	Scatter Plot of Absolute Values of Speech endpoints and Absolute Value of ALSFRS-R	Plot individual values as dots	SAC
2.86.	FAS	EFF_F2	Scatter Plot of Change from Baseline of Speech endpoints and Change from Baseline of ALSFRS-R	Plot individual values as dots	SAC
2.87.	FAS	EFF_F2	Scatter Plot of Slope of Speech endpoints and Slope of ALSFRS-R	Plot individual values as dots	SAC
2.88.	FAS	EFF_F2	Scatter Plot of Absolute Values of Speech endpoints and Absolute Values of FVC	Plot individual values as dots	SAC
2.89.	FAS	EFF_F2	Scatter Plot of Change from Baseline of Speech endpoints and Change from Baseline of FVC	Plot individual values as dots	SAC
2.90.	FAS	EFF_F2	Scatter Plot of Slope of Speech endpoints and Slope of FVC	Plot individual values as dots	SAC
ALSFRS-R					
2.91.	FAS	EFF_F1	Mean (SE) Plot of ALSFRS-R Score	
 • Paginate by Total Score, Gross Motor Domain, Fine Motor Domain, Bulbar Domain and Respiratory Domain • Only 1 y axis 	SAC
2.92.	FAS	EFF_F1	Mean (SE) Plot of Relative Rate of Decline of ALSFRS-R Score	
 • Paginate by Total Score, Gross Motor Domain, Fine Motor Domain, Bulbar Domain and Respiratory Domain • Only 1 y axis 	SAC

Exploratory: Figures					
No.	Population	IDSL / TST ID / Example Shell	Title	Programming Notes	Deliverable [Priority]
FVC					
2.93.	FAS	EFF_F1	Mean (SE) Plot of FVC	Only 1 y axis	SAC
2.94.	FAS	EFF_F1	Mean (SE) Plot of Relative Rate of FVC	Same as above	SAC

